#### 9.2.1.2. Reverse Phase Protein Assay (RPPA)

In addition to IHC, we will plan to perform other methods of assessing protein levels such as RPPA. This assay will be run by MD Anderson Cancer Center RPPA-Functional Proteomics Core Facility, website below:

<http://www.mdanderson.org/education-and-research/resources-for-professionals/scientific-resources/core-facilities-and-services/functional-proteomics-rppa-core/index.html>

Sections of the OCT embedded core biopsies will be evaluated by a pathologist to verify tumor content. Tissue will then be cut out of the OCT and protein will be extracted using standard methods. The protein will be denatured, diluted and arrayed on nitrocellulose coated slides. The slides will be probed with a set of 150 validated antibodies (including antibodies to proteins being analyzed by IHC) and spot density determined by MiroVigene software. Samples will be normalized for protein loading and concentrations will be determined using the Super Curve Fitting program. Supervised and un-supervised hierarchical clustering analysis will then be performed. This data will be compared to results derived by IHC and used to determine differences in protein expression between patients that respond to treatment and those that do not. Proteins of interest that are included in this assay are; PTEN, PI3KCA, Cyclin D1 and total and phosphorylated forms of AKT, 4E-BP1, p70-S6, ERK and MEK.

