### 13.2. Sample Size, Accrual, and Study Duration:

This study design requires a minimum of 12 and a maximum of 37 evaluable patients. In addition, we expected to accrue an additional 10% to accommodate the potential for problem cases (i.e. patients who are not evaluable for some reason). The first 45 evaluable patients will be used in the decision analysis for this part of the trial, and estimates will also be generated using all evaluable patients. We expect approximately 3 breast cancer patients to be enrolled per month. This will translate to a total of 26 months to accrue a maximum of 50 patients and allowing for the 6 months interim analysis in both Part 1 and Part 2.

The number of patients inevaluable due to screen failure was higher than expected. As such, a total of 50 patients were consented across all sites in order to enroll 37 evaluable patients

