**Correlative endpoints:**

The statistical analysis corresponding to the correlative studies will be descriptive and exploratory in nature.

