**RPPA:**

For each patient the protein intensity fold-change ratios will be calculated from the RPPA intensity values. Ratios between tumors sampled prior to initiating trametinib single agent treatment and at time of progression on either single agent trametinib or the combination (TOP/pre-treat ratio), will be calculated. These ratios will be median-centered and clustered using Cluster 2.0 software (<http://rana.lbl.gov/EisenSoftware.htm>). Student’s t-test for differences between average protein intensity ratios at these intervals will be calculated using Microsoft Excel by grouping all the ratios for individual clusters.

Table 4	Biomarker Prevalence				
	10%	20%	30%	40%	50%

HR	0.43	0.51	0.55	0.56	0.57
----	------	------	------	------	------

These results and exploratory analyses will be used in planning future studies of this

combination treatment regimen in this patient population. Biomarker analyses on required research biopsies at study entry will be conducted to assess the predictive value of PTEN and other biomarkers on patient outcome. For example, we will assess impact of PTEN status and other markers on survival outcomes as well as ORR and CBR. For survival-based outcomes, Table 4 shows detectable hazard ratios between marker groups for varying prevalence rates and at least 80% power. The Type I error constraint is quite lax in this setting, reflecting a phase II approach and relaxation of constraints but also in the univariate setting can be used to cast a wider net to capture potential markers of interest that may provide insights for the development of future biomarker-driven therapeutic strategies. Fisher exact tests will also be used to identify potential differences in ORR and CBR rates between biomarker groups as well, although depending on prevalence rates we will likely have sufficient power to only detect large differences (e.g. 35%) if we constrain Type I error to 0.05. Again, these will be largely exploratory, and lack of significant results will be viewed with caution given these limitations but will provide

**Table 1: Statistical Considerations for Biomarker Analysis.** Maximum detectable hazard ratios (HR) using one-sided log-rank test with 80% power and alpha=0.2, assuming a sample size of 37, 26 months accrual and 12 months follow-up.

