For the QTAP/Kinome assay: Paragon Algorithm software will be used to quantify changes in bound kinase levels. As seen in Table 5, a two-sided paired sample t-test will have at least 80% power to detect a 3-fold change in bound kinase levels before and after treatment with 9 patients in each group (assuming Type I error of 0.05). Based on preliminary data, we assume that 100 kinases are captured, of which 10% of them are truly differentially expressed between pre- and post- treatment and a common standard deviation of 0.95 (in log2 scale, Table 5). Given the limited paired sample size, nonparametric tests will be used (i.e. Wilcoxon signed rank test) if approximate normality is not achievable through transformation.

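### The RPPA t-test pools all protein ratios in a cluster with no allowance for several correlated ratios per patient, so its p-values can be anti-conservative

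*Combined protocol and SAP*

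**What the plan says.** Section 13.4 (Correlative endpoints, RPPA) starts at patient level: "For each patient the protein intensity fold-change ratios will be calculated from the RPPA intensity values". The ratios compare the pre-treatment sample with the sample taken "at time of progression on either single agent trametinib or the combination (TOP/pre-treat ratio), will be calculated". Then: "These ratios will be median-centered and clustered using Cluster 2.0 software". A Student's t-test follows, and the plan describes it this way: "for differences between average protein intensity ratios at these intervals will be calculated using Microsoft Excel by grouping all the ratios for individual clusters". The paragraph describes no per-patient average, mixed model or other handling of several ratios from one patient. It gives no alpha, no sidedness and no statement on pairing.

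On the number of proteins, section 9.2.1.2 says: "The slides will be probed with a set of 150 validated antibodies". The number of proteins per cluster is not given.

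The QTAP/kinome text in the same section is more specific. It names the test and the error rate (0.05): "a two-sided paired sample t-test will have at least 80% power to detect a 3-fold change in bound kinase levels". It also gives the standard deviation on the log2 scale and provides a Wilcoxon signed-rank fallback.

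The correlative section opens with a general qualifier: "The statistical analysis corresponding to the correlative studies will be descriptive and exploratory in nature".

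**The concern.** The independent unit in this trial is the patient. If all ratios in a cluster are grouped, the sample size entering the t-test becomes patients times proteins. Proteins fall in one cluster because they move together, so zero correlation within a patient is the least plausible case. The standard error is then too small and the p-value too low.

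No go/no-go rule uses this test, but its results have uses. Section 13.4 says the exploratory results will inform later studies of the combination. Section 1.2 lists molecular markers of sensitivity and resistance as a secondary objective. Section 9.2 ranks RPPA second in tissue priority, and section 9.2.1.1 lets RPPA findings choose further proteins for immunohistochemistry. A cluster wrongly flagged as changed could therefore direct both scarce tissue and later planning.

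**Working it through.** The plan states no alpha, power, sample size or error rate for this test, so there is no figure to reproduce. The check asks how far pooling moves the type I error.

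**Inputs from the documents.**
- 150 antibodies (9.2.1.2).
- At most 37 evaluable patients in Part 1 (13.2) and 32 available for Part 2 (13.3).
- The biopsy at Part 1 progression is mandatory and the one at Part 2 progression is optional (9.1). The two intervals may therefore have unequal and only partly overlapping patients.

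**Assumptions.**
- Two-sided 5% level.
- m proteins per cluster.
- Exchangeable correlation rho between proteins of one patient within a cluster.
- Correlation r between a patient's two intervals. A shared pre-treatment denominator alone gives r = 0.5 on the log scale when the variances are equal and independent.
- Median-centring is not modelled.

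**Formulas.** The true variance of the difference is V times what the pooled test assumes:
- Pooled paired test, or no between-interval correlation: V = 1 + (m − 1)·rho.
- Pooled unpaired test, same patients at both intervals: V = [1 + (m − 1)·rho]·(1 − r).
- Actual type I error = 2·[1 − Φ(1.96/√V)].

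**Worked case, m = 10, rho = 0.3.**
- V = 1 + 9 × 0.3 = 3.7, and 1.96/√3.7 = 1.02, which gives 30.8%.
- With an unpaired test and r = 0.5, V = 3.7 × 0.5 = 1.85, and 1.96/√1.85 = 1.44, which gives 15.0%.

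**Results for rho = 0.1 / 0.3 / 0.5.**

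| m | r = 0, or pooled paired | Pooled unpaired, r = 0.5, full overlap |
|---|---|---|
| 5 | 9.8 / 18.6 / 25.8% | 1.9 / 6.2 / 11.0% |
| 10 | 15.5 / 30.8 / 40.3% | 4.4 / 15.0 / 23.7% |
| 15 | 20.6 / 39.0 / 48.8% | 7.4 / 22.4 / 32.7% |

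With rho = 0 and r = 0.5, the unpaired test has an error of 0.6%. Ignoring pairing therefore lowers the error here; the inflation comes from pooling.

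**What three times nominal needs.** An error of 15% requires V of about 1.85. At m = 10 that is rho = (1.85 − 1)/9, about 0.10, when r = 0. When r = 0.5 it is rho = (1.85/0.5 − 1)/9 = 0.30.

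**Simulation check** (2,000 runs per setting, Monte Carlo standard error about 0.5 percentage points near 5%), for m = 10 and rho = 0.3:

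| Patients at the two intervals | Pooled unpaired, r = 0 | Pooled unpaired, r = 0.5 | Pooled paired |
|---|---|---|---|
| 32 and 32, full overlap | 31% | 15% | 30-31% |
| 37 and 15, the 15 a subset (15 assumed) | 32% | 23% | 31-32% |

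Partial overlap weakens the offset that an unpaired test gets from the shared baseline. One mean per patient per cluster with a paired t-test gave 4.1% to 6.0% in every setting simulated.

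**Full range.** For m from 2 to 30 and rho and r each from 0 to 0.7, the formula runs from below 1% to 67%.

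**The case against.** The strongest reply has three parts.

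First, the wording is open. A cluster might be a cluster of samples rather than of proteins. If each protein were then compared separately, the sample size would be the number of patients and there would be no pooling. But the text groups all the ratios and describes no protein-by-protein step. Pooled over a sample cluster, several ratios from one patient would still count separately. The ambiguity is a further reason to state the unit of analysis.

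Second, the correlative work is labelled descriptive and exploratory and enters no decision rule. That limits the consequence. It excuses low power or a lax alpha, but not a p-value computed on the wrong unit.

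Third, a reader might infer more than the documents support, and on these points the reply stands:
- That an unpaired test is specified, or that ratios stay untransformed. The paragraph is silent on both.
- That missing pairing adds to the inflation. With a shared baseline it works the other way.
- That a nominal 5% level is breached. None is stated for this test. The 0.05 in section 13.4 belongs to the Fisher tests and QTAP, and the log-rank table uses a one-sided 0.2.
- That 9 patients per interval applies. That is the QTAP figure.

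**Conclusion.** The concern holds in limited form. As written, the RPPA test makes no allowance for several correlated ratios from one patient and leaves pairing open. Read at an assumed two-sided 5%, its p-values can be anti-conservative, by an amount set by cluster size, within-patient correlation, between-interval correlation and patient overlap. The documents give none of these.

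For 5 to 10 proteins and rho of 0.1 to 0.5, the error is about 10-40% with r = 0 or a pooled paired test. It is about 2-24% for an unpaired test with r = 0.5 and full overlap. It is tempting to say flatly that the error is several times nominal. That is plausible for larger, tightly correlated clusters but does not hold throughout: at m = 5, rho = 0.1 and r = 0.5 the unpaired error is 1.9%. No trial decision depends on this test. What is at stake is how reliable the RPPA findings are when they are carried forward.

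**What to change.** In section 13.4, replace the grouping of all ratios with an explicit unit of analysis. Take log2 ratios and average them within each cluster to one value per patient per interval. For patients with both intervals, test across patients with a paired t-test or Wilcoxon signed-rank test. Where only some patients have the optional Part 2 biopsy, use a mixed model with a patient random effect, so that patients with one interval still contribute. State alpha and sidedness, and say whether clusters are of proteins or of samples. This brings RPPA into line with the patient-level paired test already specified for QTAP.

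False-discovery-rate control over clusters is optional in an exploratory analysis. Averaging per patient does not correct for testing clusters formed on the same data; that is a separate limitation to acknowledge when reporting.

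The cost is a few sentences of plan wording and a few lines of code, with no new data. The downside is less favourable p-values in an analysis that feeds no decision rule.

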### 1.2. Secondary Objectives

- To assess the anti-tumor activity associated with trametinib in combination with AKT inhibitor GSK2141795 after progression on trametinib in patients with metastatic TNBC.
- To determine the progression-free survival following the initiation of treatment with trametinib monotherapy in patients with metastatic TNBC.
- To determine the progression-free survival following the initiation of treatment with trametinib in combination with GSK2141795 in patients with metastatic TNBC.
- To determine the overall survival following the initiation of treatment with trametinib with GSK214179 in patients with metastatic TNBC.
- To determine the nature and degree of toxicities associated with trametinib monotherapy and trametinib in combination with GSK2141795 in patients with metastatic TNBC.
- To determine the biomarker potential of PTEN to predict response to single agent trametinib
- To determine molecular markers of sensitivity and resistance to trametinib monotherapy and trametinib in combination with GSK2141795 in patients with metastatic TNBC.

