Given the preclinical data showing that 1) RAF/MEK/ERK pathway as a mechanism of resistance to chemotherapy therapy in TNBC, 2) the enhanced effect of MEK inhibition in basal-like breast cancer models with intact PTEN (i.e. reduced PI3K/AKT pathway activity), 3) the mechanism of resistance to MEK inhibition through the PI3K/AKT pathway, 4) the 30% incidence of PTEN loss in basal-like breast cancer led to the formulation of two testable hypotheses: that single agent trametinib will demonstrate efficacy in TNBC and the anti-tumor response will depend on the PTEN status of the tumor. Moreover, the addition of AKT inhibitor GSK2141795 to trametinib will overcome intrinsic and acquired resistance to MEK inhibition.

To test these hypotheses, this is a phase II study of single agent trametinib in patients with advanced TNBC, with the addition of AKT inhibitor GSK2141795 to trametinib at time of tumor progression. This is the first trial to test the efficacy of single agent trametinib in this patient population and to determine if PTEN status will predict for response to therapy. Additionally, we will assess the ability of GSK2141795 to overcome MEK inhibitor resistance. Mechanisms of resistance to both single agent trametinib or in combination with GSK2141795 will be assessed via a comprehensive genomic and proteomic approaches on tissues collected after progression on either regimen.

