## **13 STATISTICAL CONSIDERATIONS**

### **13.1 Study Overview**

This is an open label, two-stage phase II study designed to assess the proportion of patients who have a partial or complete response to treatment with trametinib in advanced TNBC patients, followed by trametinib in combination with AKT inhibitor GSK2141795 at time of tumor progression (Figure 1, [Schema](#)). Preclinical data from the Ohio State University and others suggest that a subset of triple negative breast cancer (TNBC) patients that are PTEN wild type may demonstrate sensitivity to single agent MEK inhibition (Unpublished [name], [name]), and dual targeting of the RAS/RAF/MEK/ERK pathway and PI3K/AKT pathways may result in durable response after progression on MEK inhibitor monotherapy. Therefore, we have two parts to this study, where the primary driving hypotheses are two-fold: (1) that the anti-tumor response to the single agent trametinib will depend on the PTEN status of the tumor, with wild type PTEN having a higher likelihood of response than PTEN

null tumors; and (2) that simultaneous inhibition of the RAS/RAF/MEK and PI3K/AKT pathway with trametinib and GSK2141795 will overcome both intrinsic and acquired resistance to trametinib monotherapy. In addition to evaluating clinical efficacy of this regimen, we will also assess correlative markers in relation to clinical outcomes of interest. Part 1 focuses on evaluation of efficacy after treatment with single agent trametinib, and Part 2 is focused on evaluating salvage efficacy of treatment with the combination of trametinib and GSK2141795 in patients who progress on trametinib alone.

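### Section 13.4: Fisher's exact test for ORR and CBR by PTEN status is valid but conservative; Boschloo's exact test would keep the 0.05 level and add power at no cost in patients

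*Combined protocol and SAP*

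**What the plan says.** Section 1.2 lists as a secondary objective "To determine the biomarker potential of PTEN to predict response to single agent trametinib". Section 13.1 makes it one of two driving hypotheses and gives it a direction: "with wild type PTEN having a higher likelihood of response than PTEN" null tumors.

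The test is named in section 13.4, in the biomarker text under the RPPA heading: "Fisher exact tests will also be used to identify potential differences in ORR and CBR rates between biomarker groups as well". The same sentence adds that "we will likely have sufficient power to only detect large differences (e.g. 35%) if we constrain Type I error to 0.05". The plan gives no sidedness, base rates or numerical power for Fisher's test, and no reason for choosing it. The survival analysis of the same markers is specified as "using one-sided log-rank test with 80% power and alpha=0.2", "assuming a sample size of 37, 26 months accrual and 12 months follow-up".

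Section 13.4 also calls the correlative analyses descriptive and exploratory, and says that non-significant results will be read with caution.

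**The concern.** Fisher's test conditions on both margins of the 2×2 table. In this single-arm trial neither margin is fixed by design: the number of PTEN-null tumors and the number of responders are both random. With small groups, conditioning leaves few attainable p-values, so the true Type I error falls well below 5%. Unused error is unused power, and the plan already concedes that power is short.

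At stake is whether the trial sees a PTEN signal that is really there. Section 13.4 says that these analyses will inform the planning of future studies. An exact unconditional test uses the same 37 patients, holds the same level and is never less powerful at the splits checked below.

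**Working it through.** **Inputs**

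- N = 37 evaluable patients (sections 13.2 and 13.3; also the note to the marker table in 13.4).
- PTEN loss: "the 30% incidence of PTEN loss in basal-like breast cancer" (section 2.3). 0.30 × 37 = 11.1, so 26 wild type and 11 null.
- Other markers: the table covers prevalences of 10% to 50%, which gives splits of about 33/4, 30/7, 26/11, 22/15 and 19/18.
- Nominal level 0.05. Sidedness is not stated, so both were run.
- Response rates by PTEN status are not in the documents. They are assumed, with PTEN-null lower.

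**Formulas**

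Let a of 26 wild-type and b of 11 null patients respond, with t = a + b.

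- Fisher, one-sided: p = Σ C(26,k)·C(11,t−k)/C(37,t) over k ≥ a.
- Size at common rate π: Σ C(26,a)·C(11,b)·π^t·(1−π)^(37−t) over the rejected tables, maximised over a 1,999-point grid of π.
- Power: the same sum with a different rate in each group.
- Boschloo: order the tables by Fisher's p. The new p is the maximum over π of the probability of a table at least as extreme. Two-sided, this is either twice the smaller one-sided p (doubled version) or built directly on the two-sided Fisher p (direct version).

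**The plan's own figure**

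The 35% cannot be strictly reproduced, because no power or base rate is given. Assuming 80% power, Fisher detects 34.5 points at 19/18 with a 1% base rate. At 26/11, with base rates of 1% to 20%, it needs 38.5 to 48 points one-sided or 42.5 to 51.5 two-sided.

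**Maximum size at 26/11, nominal 5%**

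| Test | One-sided | Two-sided |
|---|---|---|
| Fisher | 2.5% | 3.0% |
| Boschloo | 4.4% | 3.9% (doubled), 4.8% (direct) |

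At a common rate of 20%, the design's alternative ORR, Fisher's two-sided size is 2.2%. No table rejected by Fisher is lost by any version of Boschloo.

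**Power at 26/11, wild type versus null, Fisher to Boschloo**

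| Rates | One-sided | Two-sided, doubled |
|---|---|---|
| 35% vs 0% | not tabulated | 59% to 74% |
| 40% vs 5% | 62% to 76% | 51% to 61% |
| 45% vs 10% | not tabulated | 45% to 53% |
| 50% vs 15% | 53% to 66% | 43% to 49% |
| 25% vs 5% | 18% to 31% | 10% to 18% |

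With the direct version the two-sided gain is 0 points for 35% vs 0%, 1 point for 25% vs 5%, and 9 to 12 points for the other three rows.

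**Hand check of the first row**

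With no responders in the null group, power is the chance that a Binomial(26, 0.35) count reaches the critical value. Fisher two-sided gives p = 0.076 at 8/26 vs 0/11 and p = 0.036 at 9/26 vs 0/11, so it needs 9 responders: 59%. The doubled Boschloo gives p = 0.039 at 8/26, so it needs 8: 74%. The direct version gives p = 0.053 at 8/26, so it also needs 9, and the gain is zero.

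**Other prevalences**

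- Fisher's maximum size, one-sided: 2.1%, 2.3%, 2.5%, 2.7% and 2.6% at 10% to 50% prevalence.
- Fisher's maximum size, two-sided: 3.1%, 3.4%, 3.0%, 4.4% and 4.0%.
- Boschloo's maximum size is at most 4.9% at every split, and no table rejected by Fisher is lost.
- Two-sided gains for 35-point differences are 0 to 5 points at 19/18. At 33/4 the doubled version gains essentially nothing when the small group is lower.
- At 26/11 with the small group higher (5% vs 40%), the doubled version gains 0.1 point.

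**Fewer usable results**

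At 22/10 (32 patients) Fisher's maximum sizes are 2.2% and 3.0%. One-sided power for 40% vs 5% goes from 50% to 68%.

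**The case against.** The strongest reply is that nothing here is wrong. Fisher's test controls the level, and whether to condition on margins that the design does not fix is a long-standing methodological choice. The plan calls the analysis exploratory, admits that only large differences are detectable, and makes the 0.05 conditional. No go/no-go rule uses this p-value, because those rules rest on response counts. All of that stands, and it is why the point is an improvement only.

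A second reply is that the gain depends on how the test is built. That also stands. The 35% vs 0% contrast gains 15 points with the doubled version and none with the direct one, and the 8/26 vs 0/11 example falls on either side of 0.05 accordingly. Naming Boschloo without its version would leave open the choice that drives the result.

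A third reply is that most contrasts shown imply an overall ORR above the design's range of 5% to 20%. For 40% vs 5% it is (26 × 0.40 + 11 × 0.05)/37 = 29.6%. The 25% vs 5% contrast, at (26 × 0.25 + 11 × 0.05)/37 = 19.1%, lies inside that range, and there power is poor with either test. The relative gain is real but the question stays largely unanswered. The plan also applies the test to CBR, where rates will be higher.

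A reader might infer that Fisher wastes half of the 5% for every marker, or that Boschloo always adds a sizeable amount. The documents do not support that. They leave sidedness open and span prevalences of 10% to 50%, and two-sided at 40% to 50% prevalence Fisher already uses 4.0% to 4.4%.

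**Conclusion.** A cheap improvement, not an error. At the PTEN split Fisher's test leaves 2.5 of the 5 percentage points unused one-sided and 2.0 two-sided. For the contrasts shown, with PTEN-null lower, Boschloo's test adds about 12 to 15 points of power one-sided. Two-sided it adds about 6 to 15 points with the doubled version and 0 to 12 with the direct one. It holds the level and loses no rejection that Fisher would make.

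This rests on 37 usable PTEN results split 26/11 and on assumed response rates. Section 9.2 foresees too few cores or limited tumor content, with archival tissue as a fallback under 9.2.1.1; fewer results would lower power for both tests. The gains should not be carried over to other markers without recalculation at their own split and direction.

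**What to change.** In section 13.4, replace Fisher's test with Boschloo's exact unconditional test at the same 0.05 level for ORR and CBR by marker group. State, before marker and response data are joined:

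- the sidedness (for PTEN, either one-sided in the hypothesised direction or two-sided);
- if two-sided, the version: twice the smaller one-sided p, or direct ordering by the two-sided Fisher p;
- the software.

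Keep the exploratory label and the caution about non-significant results.

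The cost is a line or two of text, with no added patients or assays. The downsides are that the test is less familiar to readers and that power stays low for modest ORR differences. Made after the data are joined, the same change would be a post hoc choice.
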